Placebo-controlled design was chosen because when they are utilized with randomization, they allow for valid treatment group comparisons. The disadvantage of parallel designs is that they can require large sample sizes due to the existence of both within- and between-subject variation. Cross over studies generally require fewer participants than parallel designs because each participant serves as his/her own control, thus eliminating inter-participant variation. Secondly, researchers can study individual participant response to treatment and examine participant-by-treatment interactions. Lastly, study recruitment may

be enhanced as potential participants are aware that they will receive active treatment at some point during the study.

[figure not shown]
c) End of study definition

End of study will occur once all participants have undergone both intervention and placebo arm of the study. Each subject will be enrolled for study period of 9 weeks.

6) Arms and Interventions

Study Arm Description

**FUNCTIONAL SUCRASE DEFICIENCY IN SHORT BOWEL SYNDROME PATIENTS
WITH INTESTINAL FAILURE**

Patients meeting inclusion criteria will be enrolled in the study and will provide written consent in keeping with regulations of the IRB.

Once enrolled “subjects” will be observed for 1 week on their current care and we will record:

Record daily:

Stool frequency and consistency

Side effects on sucrase – blood sugar checks by finger stick and any new symptoms – nausea, headache, etc

Emesis

Record weekly:

Ability to advance feeds

Abdominal circumference

Weight

Patient or parent perception of tolerance of feeds on sucrase by telephone questionnaire

**FUNCTIONAL SUCRASE DEFICIENCY IN SHORT BOWEL SYNDROME PATIENTS WITH
INTESTINAL FAILURE**

DAILY RECORD FOR EACH WEEK

	DAY 1	DAY 2	DAY 3	DAY 4	DAY 5	DAY 6	DAY 7
STOOL FREQUENCY							
STOOL CONSISTENCY							
SUCRASE SIDE EFFECTS							
HEADACHE (YES/NO)							
NAUSEA (YES/NO)							
ABDOMINAL PAIN (YES/NO)							
VOMITING (YES/NO)							
BLOOD SUGAR							

WEEKLY RECORD (EXCEPT WASH OUT WEEK)

	WEEK 1	WEEK 2	WEEK 3	WEEK 4
ABILITY TO ADVANCE FEEDS				
ABDOMINAL CIRCUMFERENCE				
WEIGHT				

	WEEK 6	WEEK 7	WEEK 8	WEEK 9
ABILITY TO ADVANCE FEEDS				
ABDOMINAL CIRCUMFERENCE				
WEIGHT				

**FUNCTIONAL SUCRASE DEFICIENCY IN SHORT BOWEL SYNDROME PATIENTS WITH
INTESTINAL FAILURE**

TELEPHONE QUESTIONNAIRE

	WEEK 1	WEEK 2	WEEK 3	WEEK 4	WEEK 6	WEEK 7	WEEK 8	WEEK 9

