Patient or parent perception of tolerance of feed on sucrase								

POSSIBLE ADDITIONAL TESTING

- Blood test for genetic testing if available.
- If scheduled for an endoscopy, for other medically indicated reasons as decided by the medical team, will have biopsies taken to rule out CSID.
- Breath test for functional sucrase deficiency in patients who consent.

Study Intervention Description

Subjects will be administered sucraind (sucrase) daily as instructed and followed as above. There will be a one week wash out period
During cross over subjects will be administered “placebo” daily as instructed and followed as above.

a) Intervention dosing and administration information

The recommended dosage is as follows: 1 mL (8,500 I.U.) (one full measuring scoop or 28 drops) per meal or snack for patients up to 15 kg in body weight. 2 mL (17,000 I.U.) Dosage

is 1 or 2 mL (8,500 to 17,000 I.U.) taken orally or by g-tube with each meal or snack diluted in water, milk, or infant formula. Half of the dosage will be taken at the beginning of the meal or snack and the remainder be taken during the meal or snack. The beverage or infant formula should be served cold or at room temperature. The beverage or infant formula should not be warmed or heated before or after addition of Sucraid because heating is likely to decrease potency.

b) Study Intervention Compliance

Patients will be called weekly for verification of compliance. Most patients have home nursing so their home nursing records will be reviewed as well. Finally patients will be asked to verify how much medication they have left at end of each week to assess compliance.

7) Procedures Involved

Patients meeting inclusion criteria will be enrolled in the study and will provide written consent in keeping with regulations of the IRB.

Once enrolled “subjects” will be observed for 1 week on their current care and we will record:
Record daily:

Stool frequency and consistency

Side effects on sucrase – blood sugar checks by finger stick and any new symptoms –
nausea, headache, etc

Emesis

Record weekly:

Ability to advance feeds

Abdominal circumference

Weight

Patient or parent perception of tolerance of feeds on sucrase by telephone questionnaire

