In the treatment arm of the study, subjects we will give sucrase at standard dose, 1 mL (8,500 I.U.) (one full measuring scoop or 28 drops) per meal or snack for patients up to 15 kg in body weight. 2 mL (17,000 I.U.), for a total of 4 weeks and follow patients recording stool frequency and consistency, emesis, weight, ability to advance enteral nutrition. Possible adverse effects of sucrase administration will also be recorded in addition to parental or patient perception of tolerance of feeds while on sucrase.

Give sucrase by g-tube or orally for 4 weeks

Record daily:

Stool frequency and consistency

Side effects on sucrase – blood sugar checks by finger stick and any new symptoms –
nausea, headache, etc

Emesis

Record weekly:

Ability to advance feeds

Abdominal circumference

Weight

Patient or parent perception of tolerance of feeds on sucrase by telephone questionnaire

ONE WEEK WASH OUT – no recordings

Give placebo by g-tube or orally for 4 weeks

Record daily:

Stool frequency and consistency

Side effects on sucrase – blood sugar checks by finger stick and any new symptoms –
nausea, headache, etc

Emesis

Record weekly:

Ability to advance feeds

Abdominal circumference

Weight

Patient or parent perception of tolerance of feeds on sucrase by telephone questionnaire

Possible additional tests:

Some patients will undergo blood test for genetic testing if available, those who have been scheduled for an endoscopy, for other medically indicated reasons as decided by the medical team, will have biopsies taken to rule out CSID.

Patients who consent to breath test for functional sucrase deficiency will have testing done.

Procedures:

SucraID™ (sucrase) administration:

Subject will be asked to take sucrase either orally or through g-tube with feeds daily and will be provided with this medication at no cost. Subjects will take sucrase or placebo each for 4 weeks so they will be taking additional medication daily for 8 weeks as they participate in the study.

Sucrose breath test:

This is an optional test for children over 4 years old that can cooperate by drinking a solution containing sucrose (sugar water) and breathing into a device to record components of their breath. The test will be offered free of charge to subjects in the study. This test is performed at home and the kit can be mailed back to us. The mailing costs are pre-paid. Inability to perform breath test will not eliminate subject from the study.

Endoscopy:

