Endoscopies are often performed to assess patients with short bowel syndrome with intestinal failure who are not progressing as expected. They are done to check for many things, such as, bacterial overgrowth in the intestine, inflammation in the intestine, loss of intestinal cell function, infections in the intestines etc. If a subject has had an endoscopy (obtained for clinical reasons), we will ONLY access these results for research purpose. If subject has not had an endoscopy one will only be performed if clinically indicated by medical team – we will not take additional biopsies or ask for additional tests at the time of endoscopy.

Telephone surveys:

We will conduct short telephone surveys of subject's symptoms while participating in the study. This would be similar to the phone calls they receive from the intestinal rehabilitation team about their feeds, stools, and other associated symptoms.

Medical chart review:

We will also look at recent growth chart in medical record to check growth before and during the study period, we will ask the parent or home nurse to measure abdominal circumference, weight and to check subject's blood sugars at home.

8) Outcome measures

Primary outcomes:

- Outcome Measure Title: Change in Carbohydrate Malabsorption
Outcome Measure Description: Degree of carbohydrate malabsorption will be assessed by decrease in number of stools per day.
Outcome Measure Timeframe: Baseline to Week 9
- Outcome Measure Title: Change in Carbohydrate Malabsorption
Outcome Measure Description: Degree of carbohydrate malabsorption will be assessed by change in patient symptomatology by change in score on patient symptom survey.
Outcome Measure Timeframe: Baseline to Week 9
- Outcome Measure Title: Change in Carbohydrate Malabsorption
Outcome Measure Description: Carbohydrate malabsorption will be measured by increase in growth velocity in kg/week
Outcome Measure Timeframe: Baseline to Week 9
- Outcome Measure Title: Change in Carbohydrate Malabsorption
Outcome Measure Description: Carbohydrate malabsorption will be measured by ability to advance enteral nutrition in ml/day
Outcome Measure Timeframe: Baseline to Week 9

Secondary outcomes

- Outcome Measure Title: Improved Digestion
Outcome Measure Description: Improved digestion will be measured by decreased abdominal distension/girth measured in cm
Outcome Measure Timeframe: Baseline to Week 9
- Outcome Measure Title: Improved Digestion

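### With nothing recorded in washout and no fixed day for weekly values, the second period has no assured start value for weight, girth or feed volume; the 9 weeks in section 5c also disagrees with phases that total 10

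*Protocol*

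**What the plan says.** **Duration.** Section 5c: "Each subject will be enrolled for study period of 9 weeks". Sections 6 and 7 say that subjects, once enrolled, "will be observed for 1 week on their current care and we will record" a list of daily and weekly items. Section 7 then sets out four weeks of sucrase, a one-week washout and four weeks of placebo, and confirms the medication time: "Subjects will take sucrase or placebo each for 4 weeks so they will be taking additional medication daily for 8 weeks".

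**Washout.** Section 7: "ONE WEEK WASH OUT – no recordings". The form in section 6 is headed "WEEKLY RECORD (EXCEPT WASH OUT WEEK" and has columns for Weeks 1 to 4 and 6 to 9. The telephone form has the same eight columns. Neither form has a column for the observation week, although sections 6 and 7 order weekly items in it. No day of the week is given for the weekly values.

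**Outcomes.** Section 8 names growth velocity (kg/week) and enteral advancement (ml/day) among the primary outcomes, and decreased girth (cm) among the secondary ones. All run from a single baseline to Week 9.

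**Other sources.** Under chart review, section 7 says: "We will also look at recent growth chart in medical record to check growth before and during the study period". The parent or home nurse is asked to measure weight and abdominal circumference.

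**The concern.** A crossover compares each subject with himself or herself, and section 5b gives that as the reason for the design. Three outcomes are worded as change. A change over a treatment period needs a value close to the start of that period. The first period has one, from the observation week. For the second period, the protocol says not to record in the week when such a value would be taken.

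Two things are at stake. First, the change on the second product may be measured over less than its four weeks, or from a point that mixes in the washout. Second, nobody can check from scheduled data whether feed volume and girth had returned to their starting level before the second product began. Weight gained on the first product need not be lost again, so the observation-week weight is a poor start value for the second period.

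This belongs to the protocol and not only to an analysis plan. A plan can choose a model or a summary measure, but it cannot supply a measurement that subjects were told not to take.

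The count of weeks matters less. It affects what subjects are told about duration, and which record the word baseline in section 8 refers to.

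**Working it through.** **Count of weeks.** The inputs are the phase lengths in sections 6 and 7.

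- All phases after enrolment: 1 + 4 + 1 + 4 = 10 weeks, against 9 in section 5c.
- Counted from first dose: 4 + 1 + 4 = 9. This reproduces the stated figure and fits the form numbering, but leaves out a week that the text places after enrolment.
- Observation week taken as Week 1 of the form: 3 treatment weeks remain before the Week 5 washout, so 3 + 4 = 7 medication weeks, against the stated 8.
- All phases at stated length, stopping at Week 9 from enrolment: 9 − (1 + 4 + 1) = 3 weeks of the second product, against the stated 4.
- Weeks with weekly recordings ordered: 1 + 4 + 4 = 9. Columns on the forms: 4 + 4 = 8.

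**Timing of the weekly values.** Count days from first dose. The first product runs from day 0 to 28, washout from 28 to 35, and the second product from 35 to 63. Assume that weekly values fall on the same point of each week, after d completed days (d = 0 is before the first dose on Day 1; d = 7 is the end of the week). Week k is then at day 7(k − 1) + d.

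- Week 4 = 21 + d, Week 6 = 35 + d, Week 9 = 56 + d.
- Gap from Week 4 to Week 6 = 14 days = (7 − d) on the first product + 7 of washout + d on the second.
- Span of Weeks 6 to 9 = (56 + d) − (35 + d) = 21 of 28 treatment days, for any d.

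| | End of week (d = 7) | Day 1 before dosing (d = 0) |
|---|---|---|
| Observation-week value | day 0 | day −7 |
| Week 1 | day 7 | day 0 |
| Week 4 | day 28 | day 21 |
| Week 6 | day 42, after 7 days on the second product | day 35, a true start value |
| Week 9 | day 63 | day 56; last 7 days not covered |
| Untreated value for the first period? | yes | yes |
| Untreated value just before the second? | no | yes |

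The first period has a pre-treatment value in both columns. The second has one only if d = 0. For any later day, such as d = 1 (Week 6 at day 36), the value is taken on the second product.

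With d = 7, the first period can be measured from day 0 to day 28, which is 28 of 28 days. The second can be measured from day 42 to day 63, which is 21 of 28. Starting from Week 4 instead gives day 28 to day 63, or 35 days, of which 7 are washout. A value at day 35 would give 63 − 35 = 28 of 28.

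**Age of the only other untreated value.** The observation week is days −7 to 0 and the second product starts on day 35. The value is therefore 35 to 42 days old (5 to 6 weeks) and precedes the first product.

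**The case against.** The strongest reply is that the gap depends on a day the protocol leaves open. If weekly values are taken on Day 1 before dosing, Week 6 is a start value. This stands. A reader might infer that the second period has no start value under any reading, and the text does not support that. What it supports is that no start value is assured.

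A second reply is that a crossover does not need period baselines. This also stands. Slopes over Weeks 1 to 4 and Weeks 6 to 9 rest on four values and three intervals each, like for like, and period-end feed volume and girth can be compared within subject. Measures averaged on treatment, such as stools per day, are unaffected. Daily symptom entries resume in Week 6 and allow a partial check of the return to baseline. The inference that the second period or the trial cannot be analysed is therefore unsupported. No bias or loss of precision is quantified here.

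Third, the first period has no pre-treatment velocity either, since a single observation-week weight gives no rate. That is right: the asymmetry concerns start values only. Chart review or home nursing records might supply a weight, but none is scheduled for the end of washout, and the chart review concerns growth, so it does not cover feed volume.

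Fourth, 9 weeks is coherent if counted from first dose. It agrees with the form numbering, with the time frame in section 8 and with 8 weeks of medication. A reader might infer from the mismatch that one treatment period is cut to three weeks; the stated 8 weeks of medication speaks against that. The figure missing from section 5 might label the weeks, but it would not change the wording of section 5c.

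**Conclusion.** The point holds in limited form, with medium confidence. The instruction not to record in washout, together with no fixed day for weekly values, leaves the start value of weight, girth and feed volume in the second period to chance. Unless Week 6 is taken before the first dose, these change outcomes cannot be measured over the full second period: 21 of 28 days if weekly values keep to one day. Nor can return to baseline be checked for them from scheduled data. Two of the three outcomes affected are primary. This weakens the trial without making it unanalysable, and is worth correcting because the remedy is cheap.

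The conflict between 9 and 10 weeks is real but close to editorial. Its one practical consequence is that the observation week, the natural baseline, has no column on the weekly or telephone forms.

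**What to change.** - In section 7 and on the weekly form, replace the washout instruction with one home recording of weight, girth and feed volume (ml/day) at the end of washout, before the first dose of the second product.
- State the day on which weekly values are taken. With end-of-week values, the added recording brings the second period to 28 of 28 days.
- Add a Week 0 (baseline) column to the weekly and telephone forms, and tie the baseline in section 8 to it.
- Reconcile section 5c with sections 6 to 8: either 10 weeks from enrolment, or Week 0 plus 9 weeks from first dose.

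The cost is changes of wording and forms, plus one extra set of home measurements in each of 10 subjects. Parents or home nurses already take weight and girth. Section 6b makes no exception for washout when it says "Patients will be called weekly for verification of compliance", so if that call is made in the washout week, the values can be collected then.

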Intestinal failure is a subset of patients that are dependent on parenteral nutrition for some or all of their nutrition and fluid needs. Intestinal Failure is generally categorized as occurring secondary to (1) short bowel syndrome, referring to the spectrum of malabsorption that occurs after reduction of mucosal surface area from congenital or acquired lesions; (2) dysmotility or (3) mucosal enteropathy. These patients are unable to utilize enteral nutrients to meet the demands required for normal growth and development. Usually recurrent bouts of diarrhea, vomiting, abdominal distension and/or growth failure limit the advancement of enteral feeds. Deprivation of enteral calories, often termed "gut rest" in patients failing enteral nutrition, causes atrophy of the intestinal mucosa, even in the presence of adequate PN support. This may reduce the surface area of intestinal brush border and reduce the production of disaccharidases like sucrase and their release into the intestinal lumen for carbohydrate digestion.

[figure not shown]

Figure 1: Intestinal digestion of macro and micronutrients

FORMULA	PROTEIN SOURCE	CARB SOURCE	FAT SOURCE
Similac Alimentum® (Abbott)	casein hydrolysate	sugar, modified tapioca starch	safflower oil, MCT, soy oil
EleCare® (Abbott)	amino acids	corn syrup solids	safflower oil, MCT, soy oil
Neocate Junior® (Nutricia)	amino acids	corn syrup solids	vegetable oil, canola oil, safflower oil
Splash® (Nutricia)	amino acids	maltodextrin, sugar	coconut oil, canola oil, sunflower oil
Peptamen Junior® (Nestle)	hydrolyzed whey protein	maltodextrin, sugar, cornstarch	MCT, soybean oil, canola oil

Table 1: SUCROSE IN FORMULA USED IN PEDIATRIC SHORT GUT SYNDROME

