Short bowel syndrome has a reported 5-year mortality rate as high as 30%. The incidence of necrotizing enterocolitis (NEC) is increasing with increased survival of premature babies in neonatal intensive care units and it has been estimated that 12% of infants born weighing less than 1500g will develop NEC. Approximately 25% of NEC survivors have some degree of SBS. Updated medical management of these patients have improved survival in patients with SBS and at present, the 5-year survival rates from SBS in infancy and childhood range from 73% to 89%. Increasing incidence of SBS and improving 5-year survival rates leads to increase likelihood of physicians encountering these patients at some point in their practice. The most significant sources of morbidity and mortality in children with SBS are blood stream infections and parenteral nutrition-associated liver disease. Strategies that advance

enterally feeding thus eliminating need for parenteral nutrition and need for central venous catheters can significantly improve outcomes in short bowel population.

To my knowledge there have been no studies on disaccharidases in short bowel syndrome populations or the use of disaccharidase supplementation to improve carbohydrate digestion in these patients.

4) Inclusion and Exclusion Criteria*

Inclusion:

- Short bowel syndrome, of all ages, with dependence on parental support to provide at least 50% of fluid or caloric needs.
- Must be on diet containing sucrose.
- Must be willing and able to sign informed consent
- Adult and Pediatric patients (all ages)

Exclusion:

- No current IV antibiotic administration for confirmed bout of bacteremia.
- Cannot be NPO
- Any condition, disease, illness, or circumstance that in the investigator's opinion puts the subject at any undue risk, prevents completion of the study, or interferes with analysis of the study results

5) Study Design

a) Overall Study Design (single arm, parallel, open label etc.)

Placebo controlled crossover trial.

b) Scientific rational for study design

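### Enteral advancement in ml/day: a feed gain kept through the unrecorded one-week washout counts for placebo unless change is measured within each period

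*Protocol*

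**What the plan says.** - **Design.** Section 5a: "Placebo controlled crossover trial". Section 5b justifies a crossover because "each participant serves as his/her own control, thus eliminating inter-participant variation".
- **Order.** Section 5b refers to randomization as a general rationale: "Placebo-controlled design was chosen because when they are utilized with randomization, they allow for valid treatment group comparisons". The text states no allocation to two orders. Section 7 writes out one sequence: "Give sucrase by g-tube or orally for 4 weeks", then the washout, then 4 weeks of placebo. A figure in section 5 is not shown and may add to this.
- **Washout.** Section 6: "There will be a one week wash out period". Section 7: "ONE WEEK WASH OUT – no recordings". The weekly record in section 6 covers weeks 1 to 4 and 6 to 9, so week 5 is blank.
- **Baseline.** One week of observation on current care before treatment. No second baseline is described.
- **Outcome.** Section 8, primary: "Carbohydrate malabsorption will be measured by ability to advance enteral nutrition in ml/day". Its time frame, like that of every other outcome, runs from baseline to week 9. Growth is a separate primary outcome, expressed as a rate in kg/week.
- **Start of period 2.** No section says what enteral regimen a subject is on when the second period begins.

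**The concern.** A crossover contrast is clean when the second period starts from a state comparable to the first. Stool counts may go back when treatment stops. Enteral advancement is different: it is cumulative, and the protocol wants it to last, since sections 3 and 13 give freedom from parenteral nutrition as the benefit. A volume reached on sucrase may simply be the subject's current regimen when placebo begins.

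A subject who takes placebo first carries no such gain into the sucrase period. The carry-over therefore differs by order, and randomising the order does not cancel it.

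If volume is compared as a level, or as change from the single pre-treatment baseline, sucrase gains are credited to placebo. A real benefit on a primary outcome could then be understated or missed. With 10 subjects there is little margin for that.

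**Working it through.** The protocol gives no effect size, SD, power or retained share, so there is no stated figure to reproduce. The check uses simple crossover algebra.

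**From the protocol:** 4 weekly records per period, 1 week of washout, one baseline, 10 subjects.

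**Assumed:** weekly gain off sucrase *p*; extra weekly gain on sucrase *g*; share *r* of the extra gain still present when period 2 starts.

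**Formulas** (sucrase minus placebo, ml/day)
- True effect: end of period 4*g*; mean of four records (1+2+3+4)/4 × *g* = 2.5*g*.
- Carry-over from sucrase into placebo: 4*rg*.
- Trend between periods, which start 4+1 = 5 weeks apart: 5*p*.
- Sucrase first: end 4*g* − 4*rg* − 5*p*; mean 2.5*g* − 4*rg* − 5*p*.
- Placebo first: end 4*g* + 5*p*; mean 2.5*g* + 5*p*.
- Average of both orders: end 4*g* − 2*rg*; mean 2.5*g* − 2*rg*.

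**Illustration 1:** entry volume 300, *g* = 30, *p* = 0, *r* = 1. Sucrase first gives 330, 360, 390, 420 (mean 375), then 420 throughout. Placebo first gives 300 throughout, then 330 to 420 (mean 375).

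| | Period means | End values |
|---|---|---|
| True effect | +75 | +120 |
| Sucrase first | 375 − 420 = −45 | 420 − 420 = 0 |
| Placebo first | 375 − 300 = +75 | 420 − 300 = +120 |
| Both orders averaged | (−45 + 75)/2 = +15 | (0 + 120)/2 = +60 |

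The averaged loss is 60/75 = 80% on means and 60/120 = 50% on end values.

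**Illustration 2:** end values, total gain on sucrase 20 per week, so *g* = 20 − *p*.

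| *p* | True | Sucrase first, *r* = 0 / 0.5 / 1 | Both orders, *r* = 0 / 0.5 / 1 |
|---|---|---|---|
| 0 | +80 | +80 / +40 / 0 | +80 / +60 / +40 |
| 5 | +60 | +35 / +5 / −25 | +60 / +45 / +30 |
| 10 | +40 | −10 / −30 / −50 | +40 / +30 / +20 |

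In the sucrase-first column, what is lost at *r* = 0 is period trend, not carry-over. With *p* = 0, sucrase-first period means turn negative once *r* exceeds 2.5/4 = 0.625, while end values reach zero only at *r* = 1.

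**Within-period change:** 4(*g* + *p*) on sucrase minus 4*p* on placebo = 4*g*, at every *r* and in either order. This recovers +120 in illustration 1 and +80, +60 and +40 in illustration 2. It needs a volume recorded just before period 2, which falls in the unrecorded week.

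**Scale at n = 10** (paired t-test, two-sided 0.05, assumed): a standardised effect of 1.0 has 80% power; halved to 0.5 it has 29%.

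**The case against.** The best defence is that section 8 titles the outcome as a change and speaks of ability to advance, and that the record form asks about advancement week by week. Both fit a within-period reading, under which retained volume does no harm. The baseline-to-week-9 time frame is attached to every outcome, so it may not be meant to define the contrast, and a statistical analysis plan could set that. This stands in part. Even with the present records, a slope from week 6 to week 9 could be formed, and in the model it is unbiased. But it loses the first week of period 2, and no analysis plan can recover a starting value that was not collected. The printed time frame also points away from a within-period measure.

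The second defence is that full retention is extreme. Section 3 says that diarrhea, vomiting and distension limit feeding, so volume may fall once sucrase stops. This stands: the bias shrinks with the retained share and is nil at zero.

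A reader might also infer more than the document supports:
- *That weight gained on sucrase biases the growth outcome in the same way.* The outcome is a rate, so weight merely kept does not bias it if the rate is computed within each period.
- *That the effect will be reversed.* In the balanced-order calculations it stays positive. Reversal needs the sucrase-first order together with averaging over the period or continued gains off sucrase.
- *That one week clears the enzyme, or that extra feeding lifts the subject's own sucrase for longer.* The protocol states neither. Its remark that lack of enteral calories "causes atrophy of the intestinal mucosa, even in the presence of adequate PN support" concerns withholding feeds.
- *That section 5b claims the washout makes each subject a clean control.* It makes a general statement about crossovers and does not mention the washout.

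**Conclusion.** The point holds for enteral advancement in ml/day. One baseline, an unrecorded washout and a time frame across both periods allow a kept sucrase gain to be counted for placebo. If volume is compared as a level or from the single baseline, the average over both orders loses up to half the effect on end values and up to 80% on period means. These maxima assume full retention through the washout and linear weekly gains. In the sucrase-then-placebo order the effect could vanish or reverse, partly through period trend. The protocol does not give the retained share, so the actual size is unknown.

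Within-period change removes the bias from retained volume but has its own limit. If volume falls during the placebo period itself, that fall counts against placebo and could overstate the benefit. That is one reason to show results by order.

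**What to change.** - **Section 8.** For enteral advancement, replace the baseline-to-week-9 time frame with change within each 4-week period from that period's own starting value. Compute growth velocity within each period likewise.
- **Sections 6 and 7.** Record feed volume and weight at the end of the washout, immediately before period 2, using the existing weekly record.
- **Analysis statement.** Prespecify within-period change as the main measure. Report results by treatment order and for the first period as supportive only. Do not switch to first-period data if the results disagree: such a data-dependent choice distorts the error rate, and about 5 subjects per order are too few to detect carry-over.
- **Sections 7 and 8.** Reconcile them so that the enteral regimen at the start of period 2 is documented. Its content is for the clinical team.

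**Cost:** amendment wording, one extra weekly record per subject and a small extra table. Within-period change may be somewhat noisier than a level.

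### Sections 6 and 7 give one treatment order (sucrase, washout, placebo) with no allocation step; followed as written, treatment cannot be separated from period

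*Protocol*

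**What the plan says.** - Section 5a gives the design as "Placebo controlled crossover trial". The word randomised is not in that label.
- Section 5b gives the rationale: "Placebo-controlled design was chosen because when they are utilized with randomization, they allow for valid treatment group comparisons". This is the only mention of randomisation in the protocol text, and it is a general argument, not a procedure.
- Section 6 (Study Intervention Description) has subjects take sucrase and then a one-week washout, and continues "During cross over subjects will be administered" placebo.
- Section 7 sets out the same order as consecutive steps: "Give sucrase by g-tube or orally for 4 weeks", "ONE WEEK WASH OUT – no recordings", "Give placebo by g-tube or orally for 4 weeks".
- Some sentences are neutral on order. Section 5b says participants know that "they will receive active treatment at some point during the study". Section 5c ends the study when everyone has been through both arms. Section 7 adds "Subjects will take sucrase or placebo each for 4 weeks". All of these fit a single order as well as two orders.
- Section 20 sets 10 subjects. A figure follows section 5b but is not available to this review.

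**The concern.** A two-period crossover separates treatment from time only because some subjects take the products in one order and the rest in the other. If all take sucrase first, the sucrase-minus-placebo difference is also the period 1-minus-period 2 difference. Any change over the nine weeks that has nothing to do with sucrase then enters the treatment estimate in full.

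The four primary outcomes in section 8 are exposed to different degrees:

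- **Stool count and symptom score** are levels, so any time trend biases them directly.
- **Enteral feed advancement in ml/day** is exposed in the same way if it is read as a level.
- **Growth** is a velocity in kg/week, so steady growth causes no bias. Only a change in growth rate between periods does.

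The background in section 3 describes intestinal adaptation and recurrent bouts of symptoms, so change over time is plausible. The protocol gives neither its size nor its sign. A difference in either direction could therefore not be credited to sucrase or to its absence.

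**Working it through.** The protocol states no alpha, power, SD or effect size, so there is no figure of its own to reproduce. Inputs from the protocol: 10 subjects (section 20), two treatment periods per subject (section 7), and weekly records at weeks 1–4 and 6–9 (section 6 forms). Assumed: paired t-test, two-sided 0.05. Shifts are in SDs of the within-subject difference.

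**1. Can treatment be identified?** Take 10 subject columns, one period column and one treatment column, 12 in all.

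| Allocation | Columns | Rank | Within-subject correlation, period with treatment |
|---|---|---|---|
| All 10 sucrase first | 12 | 11 | −1 |
| 5 in each order | 12 | 12 | 0 |

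With one order, the treatment effect is not estimable separately from period.

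**2. False-positive rate with no drug effect.** For the single order, a period shift d gives a noncentral t with df = 9 and noncentrality d√10.

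| Assumed shift (SD) | Single order | 5/5, period-adjusted (simulated) |
|---|---|---|
| 0 | 5% | 5% |
| 0.25 | 10.9% | 5% |
| 0.5 | 29.3% | 5% |
| 1.0 | 80.3% | 5% |

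**3. Could a trend term rescue the single order?** Set treatment = 1 in weeks 1–4 and 0 in weeks 6–9, and fit a linear week term.

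- Week sum of squares 60, treatment sum of squares 2, cross-product −10. So r² = (−10)²/(60 × 2) = 100/120 = 0.833, and variance inflation = 1/(1 − 0.833) = 6.
- SE at n = 10 is √(6/10) = 0.775 SD, so power at a 1 SD effect falls from 80% to 21%. This assumes independent weekly errors and no subject-by-treatment variation. If 25%, 50% or 75% of the variance of the difference is subject-by-treatment variation, the inflation is 4.75, 3.5 or 2.25 and power is 25%, 33% or 47%.
- A step change between periods stays in the estimate in full.

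**4. Does the untreated baseline week help?** Enter it as week 0, off treatment. The variance multiplier for the treatment effect is 0.673 against 0.500 without a trend term, a ratio of 1.35, and power at 1 SD is 68%. This requires placebo to equal no treatment and the trend to be linear. If the trend is not linear, bias remains:

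- With a step between periods, 0.42 of the step remains.
- With a plateauing trend, 1 − exp(−week/τ), scaled to a period shift of 1, the bias has the opposite sign to the unadjusted bias of −1. It is 3.35, 0.56, 0.22, 0.10 and 0.04 of the shift for τ = 1, 3, 6, 12 and 26 weeks.

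**5. Growth velocity (illustrative rates).** Steady growth of 0.10 kg/week gives 0.10 in both periods, so the bias is 0. A rate that moves from 0.125 to 0.175 kg/week between periods gives a spurious difference of 0.175 − 0.125 = 0.05 kg/week.

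**6. Cost of using both orders.** With 5/5, SE = √(1/5 + 1/5)/2 = 0.316 SD on df = 8, and power at 1 SD is 79%. A 4/6 split gives 77%. The single order with no period effect gives 80% on df = 9.

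**The case against.** The strongest counter-argument is the figure after section 5b, where a crossover schema would normally sit. It may show two randomised sequences, and its absence from the text is not a fault of the plan. Section 7 also introduces its first block as the treatment arm, so its blocks could be read as descriptions of two arms and not as a timetable. This limits what can be claimed: the documents do not establish that the trial is non-randomised. It does not remove the point. The washout line sits between the two blocks, and section 6 assigns placebo at cross-over, so the sequential reading is the natural one. Staff working from the text would give every subject sucrase first.

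A second argument is that randomisation details often sit in an SAP or pharmacy manual. That holds for list generation and concealment. It does not hold for whether order is randomised at all, which is settled by trial conduct and cannot be restored at analysis.

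Third, the trend-adjustment results depend on assumptions. This is fair: with the baseline week, power is 68%, and the plateau bias becomes small when the trend is slow. The chart review in section 8's companion procedures (section 7, medical chart review) also gives some pre-study growth data. These rescues still need an assumed trend shape, and growth history says nothing about stools, symptoms or feeds.

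**Conclusion.** The concern holds as a statement about the written procedures. Sections 6 and 7 give one order and no allocation step, which conflicts with the condition for validity in section 5b. Followed as written, treatment is completely aliased with period (rank 11 of 12), and all four primary outcomes rest on that comparison.

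The aliasing needs no numerical assumption. Its practical size does: false-positive rates of 11% to 80% follow from assumed shifts of 0.25 to 1.0 SD, and the protocol gives no basis for choosing among them. Whether the trial as conducted is aliased depends on the figure and on practice at the site. If the figure shows two sequences, the defect is a contradiction within the protocol, and sections 6 and 7 still need rewriting. This must be fixed before dosing, because it cannot be repaired afterwards.

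**What to change.** - Randomise subjects 1:1 to sucrase-then-placebo or placebo-then-sucrase from a concealed list, five per sequence, with spare entries because section 14 intends to replace withdrawals.
- Rewrite sections 6 and 7 by period (period 1 product, period 2 product) for both sequences, so that they agree with section 5b and the figure.
- Estimate the effect from within-subject differences adjusted for period. The detailed model can stay in the SAP.
- If a single order is really intended, withdraw the randomisation rationale in section 5b and state that treatment and period cannot be separated.

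The cost is a protocol amendment, a short randomisation list and one degree of freedom (8 instead of 9). Power at a 1 SD effect is 79% with a 5/5 split or 77% with 4/6, against 80%, assuming no carry-over. No extra patients, visits or drug are needed.
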